7.7 Capturing and Eliciting Adverse Event Information

7.7.1 Adverse Event Reporting

All AEs must be recorded from the time the participant is enrolled until 48 hours after the study primary endpoint.

The specific protocol-defined AEs (refer to Tables 7a) occurring in each specified time frame are to be recorded on the AE CRF within the BLUEPRINT study DMS.

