3.2 Outcomes

Table 3a defines the outcomes measures in relation to objectives and confounders.

Table 3a Listing objectives, exposure, outcomes and outcome measures, and confounders

PRIMARY OBJECTIVE
To comprehensively define the respiratory phenotype in the first 7 days after birth of preterm infants born between 22+0 and 31+6 weeks' gestation.

Exposure:
 
Day 7 after birth.

Outcome & outcome measure:
 
Functional endotypes defined from clinical, plasma protein and lung imaging measures using latent class analysis followed by external validation via group-based trajectory modelling.

Confounding factors:
 
Maternal and antenatal factors and management, clinical decisions regarding respiratory support (site and clinician differences in guidelines and management), preterm non-respiratory complications (such as infection, neurological disease, necrotising enterocolitis).

SECONDARY OBJECTIVES
To compare the respiratory endotypes associated with different respiratory outcomes using observational data at 72 hours after birth in preterm infants born between 22+0 and 31+6 weeks' gestation.

Outcome & outcome measure
 
Functional endotypes defined from clinical, plasma protein and lung imaging measures using latent class analysis (LCA) followed by external validation via group-based trajectory modelling.

To develop the first functional classification of preterm respiratory disease using a combination of clinical, lung imaging and molecular biomarkers.

Outcome & outcome measure
 
Temporally specific respiratory phenotypes derived from longitudinal latent class analysis of clinical, lung imaging and molecular biomarker data from all time points of the study.

To determine how specific early preterm phenotypes relate to a diagnosis of BPD and use this delineation to develop a predictive modelling tool for the early diagnosis of BPD.

Outcome & outcome measure

BPD status at 36 weeks' corrected PMA using Walsh Definition and Jensen Grade of Severity and functional endotypes determined above.
SECONDARY OBJECTIVES cont.
To determine how specific early preterm endotypes relate to outcomes of the primary NICU admission, including duration of invasive mechanical ventilation and supplementary oxygen support, mortality, need for supplementary oxygen at discharge home.
Outcome & outcome measure

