6.2.5 Blood Sampling and plasma isolation

Details of blood sampling and processing methodology are outlined in the BLUEPRINT Lab Processing Manual.

A minimum sample volume of 0.2ml of whole blood is required at each timepoint to perform the mass spectrometry analysis. Whole blood samples (0.5ml) will be collected into EDTA microtubes by a research or bedside nurse via either umbilical arterial line or capillary access. The required 0.2 - 0.5 ml of whole blood is consistent with the volume of blood required for common clinical investigations in preterm infants (approximately 0.3-0.5 mL for electrolyte or full blood count analysis) and represents between 0.17-0.5% of circulating blood volume (500-1500 g weight).

Blood samples will be collected at 72 hours (± 12 hours) and Day 7 (± 12 hours) post-birth from all enrolled infants. Where possible, arterial sampling will be used as this is less invasive for the infant. Capillary sampling involves breaching the skin (heel) using a micro-lancet. Micro-lancet capillary sampling is common practice in all Victorian NICUs and considered standard of care when arterial access is not available. Both arterial and capillary sampling will be conducted in accordance with current NICU blood sampling guidelines at participating sites. The ± 12 hours sampling window allows for the impact of blood sampling on the infant to be limited. Capillary blood samples will be matched to routine clinical sampling timelines to ensure there are no additional skin breaches associated with participation in the project. If routine sampling is not occurring within the allowable ± 12 -hour window, a protocol deviation will be noted in the RedCap database. All blood samples will be performed by the bedside nurse/midwife, phlebotomist or doctor who will be instructed not to persist with sampling if the procedure would expose the infant to longer distress or pain. To further ensure infant safety, a member of the study team will confirm with the clinical team the suitability of sample collection prior to each

collection based on the individual characteristics of the infant. A sample will only be taken if the treating clinician is satisfied the infant would not be harmed.

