7.1.2 Specific Protocol-Defined Adverse Events and Serious Adverse Events

It is anticipated that there will be minimal risks involved to the infants and families. However, the BLUEPRINT study population involves critically ill preterm infants that are anticipated to have a high number of AEs. Therefore, **the protocol has designated study-specific AEs that are required to be reported within a certain timeframe.** Table 7a below lists specific protocol-defined AEs and the timeframe within which they are to be reported.

Whilst there will be minimal handling associated with LUS and EIT records, study-specific AEs will be reported by the Investigator and assessed for the severity and relatedness. The potential risk of breeches in skin integrity represents a reportable protocol-defined adverse event, and specific data on skin integrity will be included in the study database, as will questions regarding tolerance of the imaging. Clinical staff and parents will be notified of any potential adverse events related to the study (including breeches of skin integrity).

Table 7a Specific Protocol-Defined AEs:

Adverse Event Definition	Reporting Time Frame
Oxygen requirement of $FiO_2 \geq 20\%$ of baseline for 2 hours or more after any imaging measurement	Within 72 hours after each scheduled lung function assessment
Breach of skin integrity or skin irritation associated with LUS or EIT	Within 24 hours of each scheduled lung function assessment
Apnoea requiring stimulation or other intervention that required the EIT or LUS scan to be terminated	Within 72 hours after each scheduled lung function assessment
Acute oxygen desaturation ($SpO_2 < 90\%$) that required the EIT or LUS scan to be terminated	Within 72 hours after each scheduled lung function assessment

Proven infection (culture or PCR positive)	Within 72 hours of a scheduled assessment involving lung function assessments or plasma measurements
--	---

The AEs outlined in Table 7a occurring in each specified time frame are to be recorded on the AE Form within the BLUEPRINT Study REDCap DMS

Any additional adverse events deemed **related or possibly related** to study assessments or procedures, as evaluated by the site PI, should also be documented on the AE form, and entered in the DMS.

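### The adverse-event recording rules contradict each other on stop date and scope, most clearly for imaging at 1 and 2 years, and the oxygen-event threshold and blood-volume share are wrong as written

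*Protocol*

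**What the plan says.** **Recording window.** Section 7.7.1 opens with "All AEs must be recorded from the time the participant is enrolled until 48 hours after the study primary endpoint". Its next sentence gives the Table 7a events their own rule: those "occurring in each specified time frame are to be recorded on the AE CRF within the BLUEPRINT study DMS".

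No section gives the primary endpoint a date. The nearest guide is Table 3a in section 3.2, where the primary objective is "To comprehensively define the respiratory phenotype in the first 7 days after birth of preterm infants" and its exposure is "Day 7 after birth". Section 11.1, however, sizes the study on BPD, which is assessed at 36 weeks' PMA.

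**Scope.** Sections 7.6 and 7.7.1 speak of all adverse events. Section 7.1.2 expects many events in this population and says that "the protocol has designated study-specific AEs that are required to be reported within a certain timeframe". It also asks for any other event that the site investigator judges related or possibly related.

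**Table 7a.** Three of its five rows carry the frame "Within 72 hours after each scheduled lung function assessment". The skin row uses 24 hours, and the infection row uses 72 hours around an imaging or plasma assessment. The oxygen row counts a requirement of FiO2 at or above 20% "of baseline for 2 hours or more after any imaging measurement".

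**Blood.** Section 6.2.5 sets a 0.2 ml minimum, plans 0.5 ml samples, and says that 0.2-0.5 ml "represents between 0.17-0.5% of circulating blood volume (500-1500 g weight"). Section 7.1 confirms 0.5 ml per sample and two samples.

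**The concern.** A site that follows the first sentence of 7.7.1 could close its adverse-event form at about Day 9. A site that follows Table 5a would stop at 36 weeks, and one that follows 6.2.8 would go on to discharge or 44 weeks' PMA. A site that follows Table 7a would record events after every scan, including those at 1 and 2 years. Sites could also differ on whether they record every event or only the designated ones.

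These data feed the annual safety report to the ethics committees (7.7.2) and the review by the data and safety monitoring committee (10.1.2). Event rates gathered under different windows and scopes cannot be pooled or compared. An oxygen event without a usable threshold cannot be counted in the same way everywhere. An understated blood share gives a wrong picture of the burden in the smallest infants.

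**Working it through.** **1. The window**

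Inputs: Day 7 is 168 hours with a window of ±12 h (Table 5a). The general cut-off is 48 h (7.7.1) and the longest post-imaging frame is 72 h (Table 7a).

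- Cut-off if the endpoint is Day 7: (168 + 48)/24 = Day 9.0, or (180 + 48)/24 = Day 9.5 at the upper limit.
- End of the 72 h frame for the Day 7 scan itself: (168 + 72)/24 = Day 10.0, or Day 10.5 at the upper limit. This is 24 h after the general cut-off.
- Table 5a has seven imaging points not marked optional: 72 h, Day 7, Day 14, Day 28, 36 weeks, Year 1 and Year 2. Five of the seven fall after Day 9.

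| Place | Adverse-event capture runs to |
|---|---|
| 7.7.1, first sentence | 48 h after an undated endpoint (about Day 9 if Day 7) |
| Table 5a, adverse-event row | 36 weeks' PMA; no mark at end of NICU stay, Year 1 or Year 2 |
| 6.2.6 | Day 14 and Day 28 |
| 6.2.8 | discharge, death, withdrawal or 44 weeks' PMA, whichever is first |
| 7.7.1, second sentence, with Table 7a | up to 72 h after each scheduled imaging assessment, no end date |

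Anchoring the endpoint at the 36-week BPD assessment covers the in-hospital scans, but the rows still disagree. The 48 h is shorter than the 72 h, 6.2.8 runs later, and Years 1 and 2 stay outside the general rule. At those two visits LUS and EIT are repeated (6.2.9, Table 5a), yet Table 5a has no adverse-event mark and the data list in 6.2.9 has no adverse-event item. Only the wording of Table 7a reaches them.

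**2. The oxygen event**

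Literal threshold = 0.20 × baseline FiO2.

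| Baseline | 20% of baseline | 20% relative rise | rise of 0.20 absolute |
|---|---|---|---|
| 0.21 | 0.042 | 0.252 | 0.41 |
| 0.30 | 0.06 | 0.36 | 0.50 |
| 0.40 | 0.08 | 0.48 | 0.60 |

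Even at a baseline of 1.0 the literal threshold is 0.20, which is below room air (0.21). An unchanged FiO2 is 100% of baseline and always meets it. If a rise is meant, the relative and absolute readings differ by 0.14 at a baseline of 0.30 (0.36 versus 0.50).

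**3. The blood share**

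Share = sample volume / (blood volume per kg × weight). The protocol gives no blood volume per kg, so I first find the value that reproduces its own figures.

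- 0.2 ml / 0.5% = 40 ml at 500 g, which is 80 ml/kg.
- 0.2 ml / 0.17% = 118 ml at 1500 g, which is about 78 ml/kg.

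Both ends of the stated range therefore come from the 0.2 ml minimum at about 80 ml/kg. With the planned 0.5 ml at 80 ml/kg:

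- 1500 g: 0.5/120 = 0.42%.
- 500 g: 0.5/40 = 1.25%, which is 2.5 times the stated maximum.
- Two samples at 500 g: 1.0/40 = 2.5%.

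The range for 0.2-0.5 ml is thus 0.17-1.25% per sample. For 0.5 ml at 500 g to be 0.5%, blood volume would have to be 0.5/0.005/0.5 = 200 ml/kg. Under an assumed 70-100 ml/kg, 0.5 ml at 500 g is 1.4% down to 1.0%.

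**The case against.** The strongest reply is that a two-tier reading works: all events for a limited early period, then the Table 7a events after every scan. The second sentence of 7.7.1 supports this. Skin injury, apnoea and desaturation are all Table 7a events, so they remain reportable at later sessions whatever the first sentence says.

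This stands, and it rules out a tempting inference: that recording stops at Day 9 and up to 3 × 550 = 1,650 later in-hospital scans go unmonitored. The Day 14, Day 28 and 36-week scans all carry an adverse-event mark in Table 5a, and 6.2.6 and 6.2.8 cover the same period. Day 7 as the endpoint is itself an inference. Follow-up visits are encouraged but not mandatory (4.2), so the Year 1 and 2 gap concerns those who attend.

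The two-tier reading does not resolve everything. The protocol never states it, it does not supply the missing date, and it conflicts with 6.2.6, 6.2.8 and Table 5a, which continue general adverse-event capture past Day 9. It also leaves Years 1 and 2 without a mark in the schedule.

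On oxygen, sites will probably read the row as a rise, so a claim that every scan will be counted as an event goes beyond what the text shows. The unclear scale remains. On blood, the actual volume and number of samples are stated openly (6.2.5, 7.1). Only the derived percentage is wrong, and it has no bearing on event counts.

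**Conclusion.** The point holds as an internal contradiction with two faulty safety figures. The recording rules give at least four different end points and two different scopes, and no reading of 7.7.1 makes them all agree. The consequence is a risk of inconsistent capture between sites, clearest at Years 1 and 2. A certain loss of procedure harms is not shown.

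The oxygen row defines no usable event as written. The blood share is understated 2.5-fold at its upper end for the planned sample at the protocol's implied 80 ml/kg (2.0- to 2.9-fold over an assumed 100 to 70 ml/kg).

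The Day 9 figure assumes that the endpoint is Day 7; the contradiction does not depend on it. None of this touches the primary outcome or its analysis. It should be corrected at the next amendment but is not of the highest severity.

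**What to change.** - Reconcile 7.7.1, 7.1.2, 7.6, 6.2.6, 6.2.8, Table 5a and Table 7a into one rule with an explicit end date or visit. Keep the start at enrolment. State whether all events or only designated and related events are recorded in each period. Make clear that Table 7a and related events are recorded after every scheduled imaging session, and add the adverse-event mark at Years 1 and 2.
- Reword the oxygen event as an increase from baseline. The investigators should state its size and whether it is relative or absolute; no threshold is proposed here.
- Restate the blood share in 6.2.5 for the 0.5 ml sample and name the assumed blood volume. At 80 ml/kg, 0.2-0.5 ml is 0.17-1.25% per sample at 500-1500 g, and two 0.5 ml samples at 500 g total 2.5%.

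The cost is a protocol and form amendment and a little more adverse-event entry. Events arising after the Year 1 and 2 visits would rely on parent report, because the children are no longer in hospital.

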7.7.2 Coordinating Principal-Investigator Reporting Procedures

The Coordinating Principal-Investigator (CPI) (or delegate) is responsible for:

- Implementing and maintaining a suitable recording system to record information from all AEs received from participating sites.
- Ensuring that the CPI is notified of each AE to enable the AE to be assessed by the CPI and any other appropriate reviewers for nature (expected/unexpected), and causality.
- Reporting AEs to ethics committees according to applicable local laws.
- Considering information provided by (non-serious) adverse event data.
- Informing each participating site of new information arising from serious and non-serious adverse events that may affect the conduct of the Study, or the rights, interests, safety, or wellbeing of study patients.
- Providing any updated safety information to all Site PIs.

The Coordinating Principal-Investigator (or delegate) is also responsible for providing the following additional safety information to the approving HRECs:

1. Provide an annual safety report, including a summary of the evolving safety profile of the study.

7.7.3 Potential Risks Related to Study Conduct

Risks to the successful conduct of the study are low. The study has obtained NHMRC-funding to conduct the study to the 2-year follow-up endpoint.

1. **Recruitment:** Sites have active and established neonatal research programs with extensive experience in recruiting families of different ethnicities and sociodemographic backgrounds during times of stress associated with preterm birth. Many preterm infants are eligible for multiple unrelated studies, we have established cooperative systems at all sites of approaching families to minimise their burden, whilst maintaining high recruitment rates.
2. **Attrition at 2-year follow up:** From experience, these families are highly motivated. We will maximise follow-up rates using proven strategies which include contact by experienced staff who have known the families from birth (often involved in recruitment), having multiple alternative contacts in addition to parents, social media, and maintaining up-to-date contact details through regular contact with families via newsletters and birthday cards. We will consider the need for multiple imputation to account for missing data, if necessary.
3. **Delays in ethics approvals and multisite agreements:** We are familiar with the local HREC processes and staff. Ethics submissions will be prioritised to ensure timely processing.
4. **Death before a Scheduled Assessment:** If a participating infant passes away, then data already collected will be used, however, parents will not be asked to participate in any subsequent assessments or data collection. The research coordinators will check the infant's tertiary hospital medical records prior to contacting families to arrange follow-up appointments to ensure, where possible, that the current status of an infant is known, particularly for deceased infants.

8 DATA AND INFORMATION MANAGEMENT

8.1 Overview

The Study Investigators are responsible for storing essential study documents relevant to data management and maintaining a site-specific record of the location(s) of the site's data management-related Essential Documents.

Site Principal Investigators are responsible for maintaining adequate and accurate source documents that include all key observations on all participating infants at their site. Source data will be attributable, legible (including any changes or corrections), contemporaneous, original, accurate, complete, consistent, enduring and available. Changes to source data (hardcopy and electronic) must be traceable, must not obscure the original entry, and must be explained where this is necessary. A site-specific **Source Document Plan** will be maintained to indicate the location(s) of source documents.

The Site PI will also maintain accurate data collection forms (also known as case report forms - CRFs) and be responsible for ensuring that the collected and reported data is accurate, legible, complete, entered into the study database in a timely manner and enduring. To maintain the integrity of the data, any changes to data (hardcopy and electronic) must be traceable, must not obscure the original entry, and must be explained where this is necessary.

Any person delegated to collect data, perform data entry or sign for data completeness will be recorded on the delegation log and will be trained to perform these study-related duties and functions.

Full details of all processes are provided in a separate study-level **Data Management Plan**.

8.2 Data management

8.2.1 Data generation (source data)

In this study, the following types of data will be collected:

- Personal identifying information (names, dates of birth, contact details, postcode, URN/MRN).
- Sensitive information including health data relating to the antenatal and postnatal (NICU) period from both infant and mother.
- Respiratory and general health status at 1 and 2 years of age (including details of hospital and health care service presentations between initial NICU (birth) admission and 2 years).
- Plasma samples collected at 72 hours and 7 days.
- LUS and EIT imaging data as detailed in schedule of assessments table.

8.2.2 Source Document Plan

The source documents for this study include the participating sites' electronic/paper medical record, questionnaires completed by the infant's parent/legal guardian and/or researcher (paper); recorded data from automated instruments, laboratory reports and the signed parent/legal guardian information and consent forms. Each site participating in the study will maintain a site-specific **Source Document Plan** that will document the source, i.e. original recording, for each data discrete item/category of items collected for the study. This Source Document Plan, signed and dated by the PI, will be prepared prior to recruitment of the first infant and will be filed in the site's Investigator Site File.

8.2.3 Data capture methods and data use, storage, access, and disclosure during the study

The Data Coordinating Centre (DCCe) provides a REDCap DMS for the secure entry and storage of BLUEPRINT data. REDCap (Vanderbilt University, Nashville, TN) is a secure, web-based software platform designed to support data capture for research studies, providing:

1. an intuitive interface for validated data capture;
2. audit trails for tracking data manipulation and export procedures;
3. automated export procedures for seamless data downloads to common statistical packages; and
4. procedures for data integration and interoperability with external sources (34).

Reasons for non-participation will be documented. Access to the BLUEPRINT REDCap database will be granted to individual participating site users by the DCCe Data Manager or Central Study Coordinator.

Participating site clinical teams/study teams will enter study data directly into the secure BLUEPRINT study DMS.

Designated and authorised participating site staff must complete the CRFs and supporting documentation for each infant within a timely manner of each assessment occurring. All staff delegated by the Site PI to enter data must be indicated on the Site Signature and Delegation of Authority Log.

Study related essential documents maintained for the study will be filed within the BLUEPRINT electronic Study Master File (eTMF) platform, Florence eBinders™, a cloud-based SaaS software maintained by Florence Healthcare, hosted in Germany, EU via Amazon Web-Services (AWS) and backed up daily.

Investigator Site Files (ISF) pertaining to each participating site will also be maintained electronically via the Florence eBinders™ platform by each participating site, to enable remote monitoring of essential study and regulatory documentation.

Full information on the data variables is in the Study Data Management Plan.

8.3 Image reporting

8.3.1 Lung ultrasound aeration score

Ultrasound images will be reported using our scoring system that has been validated against gold standard measures of lung volume (Figure 8a).⁽³⁵⁾

This score ranges from 0-5 (0; worst aeration, 5; best aeration). The total scores for LUS images will range from 0-30 (categorical ordinal variable).

[figure not shown]
[figure not shown]
[figure not shown]
[figure not shown]
[figure not shown]
[figure not shown]
		

Score 0
 
 ○ No pleural line ○ No speckling ○ No A lines ○ Fully hepatized appearance 	
Score 1
 
 ○ No pleural line ○ > 50% of lung fields speckled ○ No A lines 	
Score 2
 
 ○ Broken pleural line ○ < 50% of lung field speckled ○ No A lines
		

Score 3
 
 ○ Thickened pleural line ○ No A lines ○ Coalescing B lines ○ No speckling 	
Score 4
 
 ○ Bright pleural line ○ A lines partially obscured ○ > 3 separated B lines ○ No speckling 	
Score 5
 
 ○ Well-defined, bright intact pleural line ○ A lines prominent ○ Minimal B lines ○ No speckling

Figure 8a Lung ultrasound scoring system.

